4.4 Analysis of Efficacy

The primary population for assessment of efficacy will be the mITT Population

4.4.1 Primary Efficacy Endpoint

4.4.1.1 Primary Efficacy Endpoint Definition

The primary efficacy variables are Schiff sensitivity score, tactile threshold (g), and the number of sensitive teeth (defined as number of teeth with Schiff sensitivity score ≥ 1) at Day 0 (Baseline), Day 3, Weeks 2, 4, and 8.

Schiff sensitivity score and tactile threshold will be derived as the average score of the two test teeth. In addition, for tactile threshold (g), the tooth recorded as >20 g (for screening and baseline) or >80 g (for post baseline) will be rounded up to the next increment of 10 g for the calculation of average tactile threshold (g).

Descriptive statistics (n, mean, SD, standard error [SE], median, minimum, and maximum) will be presented for Schiff sensitivity score calculated as the average score of the two test teeth at each assessment time point in Table 14.2.2.1.1 for all subjects in mITT population by study product. Raw means (\pm SE) of the Schiff sensitivity score at each time point will be plotted by study product in Figure 14.2.2.1.1 for all subjects in mITT population.

Similar to Schiff sensitivity score, other primary efficacy endpoints will also be summarized in Table 14.2.2.2.1 and Table 14.2.2.3.1 (for tactile threshold (g) and number of sensitive teeth, respectively) and in Figure 14.2.2.2.1 and Figure 14.2.2.3.1 (for tactile threshold (g) and the number of sensitive teeth, respectively) for subjects in mITT Population.

Individual Schiff sensitivity score and tactile threshold (g) data will be listed for each subject by visit and study product group in Listing 16.2.6.1 and Listing 16.2.6.2, respectively, for all randomized subjects. The number of sensitive teeth will be listed by subject, visit and study product group in Listing 16.2.6.3 for all randomized subjects.

4.4.1.2 Statistical Hypothesis, Model, and Method of Analysis

The analysis of primary efficacy endpoints will descriptively and visually present the performance of the study products over time. No formal statistical analysis is planned for assessment of primary efficacy endpoints.

3% PVM/MA + 5% KNO₃ Toothpaste
218220

4.4.1.3 Supportive Analyses

If there is more than 10% difference in the overall number of subjects between PP and mITT Populations, a summary of the Schiff Sensitivity Score, tactile threshold (g) and number of sensitive teeth will be presented for the PP Population in Table 14.2.2.1.2, Table 14.2.2.2.2, and Table 14.2.2.3.2, respectively. In addition, Schiff sensitivity score (Figure 14.2.2.1.2), tactile threshold (g) (Figure 14.2.2.2.2) and number of sensitive teeth (Figure 14.2.2.3.2) at each time point will be plotted by study product in for all subjects in PP Population.

4.4.2 Secondary Efficacy Variables

4.4.2.1 Analysis of Secondary Objectives

4.4.2.1.1 Secondary Efficacy Endpoint 1 Definition

The first secondary endpoint is change from baseline in Schiff sensitivity score at Day 3, Weeks 2, 4, and 8. Change from baseline will be derived for the individual teeth first before calculating the average change for the two test teeth.

Descriptive statistics (n, mean, SD, Standard Error [SE], median, minimum, and maximum) will be presented for change from baseline in Schiff sensitivity score at each assessment time point in Table 14.2.2.1.1 for all subjects in mITT Population by study product. Figure 14.2.2.1.1 presents raw mean (\pm SE) at each timepoint for mITT Population.

4.4.2.1.2 Statistical Hypothesis, Model and Method of Analysis

Study product differences will be tested under the null hypothesis:

- H_0 : there is no treatment difference
- H_1 : there is a treatment difference

The following study product comparisons will be analyzed:

- Test product versus negative control
- Test product versus comparator 1
- Test product versus comparator 2

Change in Schiff sensitivity score at Day 3, Weeks 2, 4, and 8 will be analyzed using an Analysis of Covariance (ANCOVA) model which will include study product as a factor and baseline Schiff sensitivity score as a covariate. Since the baseline Schiff sensitivity score will be included as a covariate, the baseline Schiff stratification value will not be included in the model.

Using the above model, adjusted mean change from baseline, along with 95% CIs will be reported by study product group. P-values testing for non-zero change from baseline will be presented for both study product groups. Mean difference between study product groups, 95% CIs and p-values will be provided for Schiff sensitivity score in Table 14.2.2.4.1. Significance

3% PVM/MA + 5% KNO₃ Toothpaste
218220

testing will be conducted at the two-sided 5% significance level; no adjustment for multiple comparisons will be made.

The assumption of normality and homogeneity of variance in the ANCOVA model will be investigated, and if violated, an appropriate data transformation or non-parametric method, for example, the van Elteren test, adjusting for baseline Schiff stratification, will be performed.

4.4.2.2 Secondary Efficacy Variable 2

4.4.2.2.1 Secondary Efficacy Endpoint 2 Definition

The second secondary endpoint is change from baseline in Tactile threshold (g) at Day 3, Weeks 2, 4, and 8. Change from Baseline will be derived for the individual teeth first before calculating the average change for the two test teeth. The tooth recorded as >20 g (for screening and baseline) or >80 g (for post baseline) will be rounded up to the next increment of 10 g for the calculation of change from baseline in tactile threshold (g).

Descriptive statistics (n, mean, SD, SE, median, minimum, and maximum) will be presented for change from baseline in Tactile threshold (g) at each assessment time point in Table 14.2.2.2.1 for all subjects in mITT Population by study product. Figure 14.2.2.2.1 presents raw mean (\pm SE) at each timepoint for mITT Population.

4.4.2.2.2 Statistical Hypothesis, Model and Method of Analysis

Study product differences will be tested under the null hypothesis:

- H_0 : there is no treatment difference versus the alternate hypothesis
- H_1 : there is a treatment difference

The following study product comparisons will be analyzed:

- Test product versus negative control
- Test product versus comparator 1
- Test product versus comparator 2

Change from baseline in tactile threshold (g) will be analyzed at Day 3, Weeks 2, 4, and 8 using an ANCOVA model with study product and baseline Schiff stratification included as factors and baseline tactile threshold (g) included as a covariate.

Using the above model, adjusted mean change from baseline, along with 95% CIs will be reported by study product group. The adjusted means will be derived using weighted model effects for the baseline Schiff stratification which are proportional to the split between strata observed in the data. P-values testing for non-zero change from baseline will be presented for both study product groups. Mean difference between study product groups, 95% CIs and p-values will be provided for tactile threshold (g) in Table 14.2.2.4.2. Significance testing will be conducted at the two-sided 5% significance level; no adjustment for multiple comparisons will be made.

3% PVM/MA + 5% KNO₃ Toothpaste
218220

The assumption of normality and homogeneity of variance in the ANCOVA model will be investigated, and if violated, an appropriate data transformation or non-parametric method, for example, the van Elteren test, adjusting for baseline Schiff stratification, will be performed.

4.4.2.3 Secondary Efficacy Variable 3

4.4.2.3.1 Secondary Efficacy Endpoint 3 Definition

The third secondary endpoint is change from baseline in DHEQ at Day 3, Weeks 2, 4, and 8.

The following DHEQ-15 endpoints will be reported:

- Responses to Questions 1 to 6, DHEQ Section 1 at baseline (as separate questions);
- Responses to Questions 7, 8 and 9, DHEQ Section 1 (as separate questions);
- Total Score for Questions 1 to 15, DHEQ Section 2;
- Restrictions Domain (total score for Questions 1 to 3, DHEQ Section 2);
- Adaptation Domain (total score for Questions 4 to 6, DHEQ Section 2);
- Social Impact Domain (total score for Questions 7 to 9, DHEQ Section 2);
- Emotional Impact Domain (total score for Questions 10 to 12, DHEQ Section 2);
- Identity Domain (total score for Questions 13 to 15, DHEQ Section 2);
- Change from Baseline at Day 3, and Weeks 2, 4, and 8 for each DHEQ endpoint.

Descriptive statistics (n, mean, SD, SE, median, minimum, and maximum) will be presented for observed scores and change from baseline for each DHEQ endpoint by study product group in Table 14.2.3.1 (For DHEQ Section 1, Q1 to Q6), Table 14.2.3.2 (for DHEQ Section 1, Q7 to Q9) and Table 14.2.3.3 (for DHEQ Section 2) for all subjects in mITT Population. Individual DHEQ scores will be listed in Listing 16.2.6.4 (for DHEQ Section 1) and Listing 16.2.6.5 (for DHEQ Section 2) for all randomized subjects.

4.4.2.3.2 Statistical Hypothesis, Model and Method of Analysis

No formal statistical analysis is planned for assessment of DHEQ endpoints.

4.4.2.4 Secondary Efficacy Variable 4

4.4.2.4.1 Secondary Efficacy Endpoint 4 Definition

The fourth secondary endpoint is changes in self-perceived discomfort associated with tooth sensitivity, as measured by a NRS, at Day 3 and Weeks 2, 4, and 8.

The 11-item NRS is a segmented numeric version of the Visual Analog Scale (VAS) in which a respondent selects the number (0 to 10) that best reflects the intensity of the discomfort caused by their sensitivity. Similar to the VAS, the NRS is anchored by terms describing discomfort extremes and ranges from 0 = no discomfort to 10 = worst discomfort imaginable.

3% PVM/MA + 5% KNO₃ Toothpaste
218220

Descriptive statistics (n, mean, SD, SE, median, minimum, and maximum) will be presented for observed NRS and change from baseline in NRS at each assessment time point by study product group in Table 14.2.4.1 for all subjects in mITT Population. Individual NRS data will be listed in Listing 16.2.6.6 for all randomized subjects. In addition, raw mean (\pm SE) of NRS will be plotted over time (Figure 14.2.4) for mITT Population.

4.4.2.4.2 Statistical Hypothesis, Model and Method of Analysis

No formal statistical analysis is planned for assessment of NRS.

4.4.3 Pharmacokinetic (Secondary)

NA.

4.4.4 Handling of Missing Values/Censoring/Discontinuations

Subjects who withdraw from the study early will be included in the statistical analysis up to the point of withdrawal. Subjects who withdraw will not be replaced. Data will not be imputed in the case of dropouts or missing data.

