## 5.5 Lifestyle Considerations

If, in the opinion of the investigator or medically qualified designee, a subject has not complied with a study restriction (oral hygiene, dietary or alcohol-related) prior to a study visit, every effort will be made to reappoint them within permitted visit tolerances (see Schedule of Activities, Table 1-1)). The reason for re-appointment will be documented in the eCRF. If this is not possible, the following visit specific actions should be taken.

- **Screening (Visit 1):** if the subject cannot be reappointed, they will be withdrawn from the study (Section 7.1). No clinical assessments will be performed. The subject may be replaced.
- **Baseline (Visit 2):** if the subject cannot be reappointed, they will be withdrawn from the study (Section 7.1). No clinical assessments will be performed. The subject will not be replaced.
- **Day 3 (Visit 3):** the subject will continue in the study. No clinical assessments will be performed.
- **Weeks 2 and 4 (Visits 4-5):** if the subject cannot be reappointed (within the visit tolerance for Visits 4-6), they will continue in the study. No clinical assessments will be performed.
- **Week 8 (Visit 6):** if the subject cannot be reappointed, they will be withdrawn from the study (Section 7.1). No clinical assessments will be performed. The subject will not be replaced.

Property of GSK Consumer Healthcare - Confidential

May not be used, divulged, published or otherwise disclosed without the consent of  
 GSKCH

CCI ██████████ Clinical Protocol Template v7.0

Page 32 of 100

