#### **Change from Baseline in Schiff sensitivity score at Day 3, Weeks 2, 4 and 8**

The Schiff sensitivity score is derived as the average score of the two test teeth. The change from Baseline is derived for the individual teeth first before calculating the average change of the two test teeth. The change in Schiff sensitivity score will be analysed at each time point using an ANCOVA model which will include product as a factor and Baseline Schiff sensitivity score as a covariate. Note that since the Baseline Schiff sensitivity score will be included as a covariate, the Baseline Schiff stratification value will not be included in the model.

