#### **Change from Baseline in tactile threshold (g) at Day 3, Weeks 2, 4 and 8**

Tactile threshold (g) and change from Baseline will be derived as for the Schiff sensitivity score. The change in tactile threshold (g) will be analysed at each time point using an ANCOVA model with product and Baseline Schiff stratification included as factors and Baseline tactile threshold included as a covariate.

For both Change from Baseline in Schiff sensitivity score and Change from Baseline in tactile threshold, using the above models, adjusted mean change from Baseline, along with 95% CIs will be reported by product group. P-values testing for non-zero change from Baseline will also be presented for each product group. Mean difference between product groups, 95% CIs and p-values will also be provided. Significance testing will be conducted at the two-sided 5% significance level; no adjustment for multiple comparisons will be made.

Property of GSK Consumer Healthcare - Confidential

May not be used, divulged, published or otherwise disclosed without the consent of  
 GSKCH

CCI

Clinical Protocol Template v7.0

Page 80 of 100

In each case, the assumptions of the ANCOVA model will be investigated. An appropriate data transformation or non-parametric method may be performed in case of strong model violations.

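### The two secondary change endpoints are analysed one visit at a time on available subjects, so earlier scores do not inform a missed later visit; one repeated-measures model would link the visits at low cost

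*SAP*

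**What the plan says.** Protocol 12.3.2 states for Schiff: "The change in Schiff sensitivity score will be analysed at each time point using an ANCOVA model". For tactile threshold it says "The change in tactile threshold (g) will be analysed at each time point using an ANCOVA model". SAP 4.4.2.1.2 and 4.4.2.2.2 carry this over: "Change in Schiff sensitivity score at Day 3, Weeks 2, 4, and 8 will be analyzed using an Analysis of Covariance (ANCOVA) model" and "Change from baseline in tactile threshold (g) will be analyzed at Day 3, Weeks 2, 4, and 8 using an ANCOVA model". The Schiff model contains product and baseline Schiff score. The tactile model contains product, Schiff stratum and baseline threshold. Neither has a visit or subject term, so each visit is fitted on its own.

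On missing data, SAP 4.4.4 says "Data will not be imputed in the case of dropouts or missing data", as does Protocol 12.3.7 in substance. Withdrawn subjects count up to withdrawal and are not replaced. The only missing-data sensitivity analysis mentioned is a possible one for pandemic-related dropout (SAP 4, Data Analysis).

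Protocol 5.5 produces gaps by rule after a lifestyle lapse:
- Day 3: "the subject will continue in the study. No clinical assessments will be performed".
- Weeks 2 and 4, if reappointment fails: "they will continue in the study. No clinical assessments will be performed".
- Week 8: "if the subject cannot be reappointed, they will be withdrawn from the study (Section 7.1). No clinical assessments will be performed".

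The medication rule in Protocol 6.8 works the other way and keeps the post-baseline sensitivity assessments.

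**The concern.** One examiner scores the same two teeth in the same subject at every visit, so a subject's Day 3, Week 2 and Week 4 scores say something about an unobserved Week 8 score. Visit-wise ANCOVA cannot use this. Two things follow. Some precision is lost at any visit with missing assessments. And if loss depends on earlier response, and does so differently between the compared products, the adjusted difference at that visit is biased even though the data needed to correct it were collected.

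There is little slack. About 120 subjects are randomised for about 30 evaluable in each of four groups (Protocol 12.1, SAP 1.4), which leaves no allowance for loss. The results are also meant to guide later studies, so a distorted Week 8 contrast would carry forward.

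**Working it through.** **Inputs from the documents.** SD of Week 8 Schiff change 0.7; 30 evaluable per group; four groups; two-sided 5% (Protocol 12.1 and 12.3.2, SAP 1.4).

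**Assumed, because the documents give none.** Fraction f missing at Week 8: 5%, 10%, 20%. Equal correlation ρ between visits after adjustment for baseline: 0.5 or 0.7. The loss mechanisms are as described below.

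**The plan's own figure.** Half-width for one group = t(0.975, 29) × 0.7/√30 = 0.2614. This reproduces the stated ±0.261. With 30 randomised and 10% or 20% lost, it becomes ±0.277 or ±0.296.

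**Between-product half-width with no loss.** t(0.975, 115) × 0.7 × √(2/30) = 1.981 × 0.7 × 0.2582 = 0.358.

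**Precision under random loss.**
- Planned variance of a Week 8 mean: σ²/[n(1−f)].
- Repeated-measures variance, approximately: (σ²/n)[R² + (1−R²)/(1−f)], where R² is for Week 8 on the three earlier visits.
- R² = 3ρ²/(1+2ρ): 0.75/2 = 0.375 at ρ = 0.5, and 1.47/2.4 = 0.6125 at ρ = 0.7.
- The ratio of the two variances is 1 − f·R², so the proportional cut is f·R².

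Planned half-widths use 4n(1−f) − 5 df; repeated-measures half-widths use 115 df.

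| f | Variance cut (ρ 0.5 / 0.7) | Effective n per group: planned → repeated measures | Half-width of difference: planned → repeated measures |
|---|---|---|---|
| 0 | 0 / 0 | 30 → 30 / 30 | 0.358 → 0.358 / 0.358 |
| 5% | 1.9% / 3.1% | 28.5 → 29.0 / 29.4 | 0.368 → 0.364 / 0.362 |
| 10% | 3.8% / 6.1% | 27.0 → 28.1 / 28.8 | 0.378 → 0.370 / 0.366 |
| 20% | 7.5% / 12% | 24.0 → 25.9 / 27.4 | 0.401 → 0.385 / 0.375 |

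A simulation of four groups of 30 (1000 runs per setting, unstructured covariance by maximum likelihood) gave cuts of 1.3% and 3.2% at 5% loss, 3.5% and 8.9% at 10%, and 9.2% and 11.0% at 20%, for ρ = 0.5 and 0.7.

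**Bias, loss in one arm only.** Let Week 8 loss follow a logistic rule in the standardised Week 4 score. Bias = ρ × 0.7 × the shift in mean standardised Week 4 score among those retained.

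| Slope per SD | Loss in that arm | Shift | Bias at ρ 0.5 / 0.7 |
|---|---|---|---|
| 1 | 10% | 0.091 | 0.032 / 0.044 |
| 1 | 20% | 0.173 | 0.061 / 0.085 |
| 1.5 | 10% | 0.122 | 0.043 / 0.060 |
| 1.5 | 20% | 0.227 | 0.079 / 0.111 |

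The range is 0.03-0.11, or about 9-31% of 0.358. Using the earlier visits, simulated bias was under 0.003 at slope 1.5.

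**Bias, same rule in both arms.** If the arms have the same Week 4 mean, the shifts cancel. If the products already differ by 0.4 at Week 4, only the difference between the two shifts remains. At slope 1 it is 0.039 (10% average loss) or 0.063 (20%), giving a bias of 0.014-0.031. At slope 1.5 it is 0.067 or 0.104, giving 0.023-0.051. The four-group simulation with one rule in every arm found 0.00-0.03 for visit-wise ANCOVA and −0.01 to 0.02 for repeated measures (Monte Carlo error about 0.006).

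**Complete-data check.** With product and baseline both crossed with visit, the repeated-measures estimates equal the visit-wise ANCOVA estimates to rounding error. For tactile threshold this holds only if Schiff stratum is also crossed with visit; with a single common stratum term the estimates differ.

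**The case against.** The plan is not unreasonable for an exploratory trial, and several points against the concern stand.

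- **Available cases, not complete cases.** A reader might infer that a subject who misses one visit is dropped throughout. The documents do not say so: each observed value is used at its own visit, and withdrawn subjects count up to withdrawal. Only the link between visits is lost.
- **The 5.5 gaps need not bias anything.** A reader might infer that these rules remove poor responders. They apply to oral hygiene, dietary and alcohol lapses, after every effort to reappoint. Nothing ties such lapses to earlier Schiff scores.
- **One-arm loss is hypothetical.** The ANCOVA terms already cover missingness that depends on product or baseline. Products that cannot be made identical in taste and appearance (Protocol 4.2), alongside a negative control, make differential loss conceivable, but the documents describe no such mechanism.
- **The primary profile is unaffected.** It rests on raw means and plots without a model (SAP 4.4.1.2), and no formal success criterion depends on the secondary tests.
- **The replacement is not free.** It adds joint normality across visits, a 4 × 4 covariance (10 parameters) and reliance on missing at random. Tactile threshold moves in 10 g steps and is capped above 80 g, so normality is a real question there.
- **Discontinuations are already tabulated** by product and reason (SAP 4.1.1).

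These limit the size of the point. They do not remove it: the model needs no extra data, and nothing planned uses earlier visits when a later one is missing.

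**Conclusion.** The point holds as a low-cost improvement to the analysis of two secondary endpoints. The precision gain is modest and depends wholly on how much is missing: none with complete data, about 2-6% of the Week 8 variance at 5-10% random loss, up to 12% at 20%. The stronger reason is protection against differential loss, worth roughly 0.03-0.11 Schiff units if 10-20% loss in one arm depends on the Week 4 score. Where both arms share the same rule, the bias at stake is near zero to about 0.03, reaching 0.05 only with slope 1.5, 20% loss, correlation 0.7 and a 0.4 difference already present at Week 4.

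Loss rates, correlations and mechanisms are all assumptions. The documents do not support saying that the planned Week 8 comparison is biased; they show only that it has no protection if loss turns out to be differential. No bias is given for tactile threshold, because the documents state no SD for it.

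**What to change.** Before unblinding, amend the SAP for change in Schiff score and change in tactile threshold:

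- Fit one repeated-measures model per endpoint with product, visit, product × visit and baseline × visit, unstructured covariance and Kenward-Roger degrees of freedom. State in advance the covariance structure to use if the model does not converge.
- For tactile threshold add Schiff stratum and stratum × visit, and keep the strata-proportional adjusted means of SAP 4.4.2.2.2.
- Report the same adjusted means, product differences and confidence intervals at each visit.
- Keep visit-wise ANCOVA, with its van Elteren fallback, as a sensitivity analysis.
- Tabulate missed assessments by visit, product and reason, including those arising under Protocol 5.5. No change to the 5.5 rules is proposed.
- Record the departure from Protocol 12.3.2 in SAP Section 5, which now reports no changes.

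The cost is SAP wording, one additional model per endpoint and the convergence plan. No extra subjects, visits or alpha are needed. The remaining weakness is that the model relies on missing at random and joint normality, which is why the visit-wise analysis should stay alongside it.

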4.5 Analysis of Safety

All safety data will be reported for the Safety Population as per actual study product received. The safety profile of the study products will be assessed with respect to AEs, OST and OHT findings

